#### **6.2.6.2 Measurements of Treatment Compliance**

The by-subject listing of treatment compliance is provided for the safety analysis set, and displays results for treatment compliance parameters in separate columns: average exposure (tablets per month; see Section 6.2.6.1) for DB, OL rimegepant, and DB or OL rimegepant;

percentage for tablet count compliance and odd study drug dosing day compliance; flags for the other parameters (“Y” or missing).

  - All the time. Defined as as-treated treatment group not equal to as-randomized treatment group, i.e., any of the following:
    - Randomized to rimegepant who took (1)  $\geq 1$  tablet from a DB placebo wallet, and (2) no tablets from a DB rimegepant wallet
    - Randomized to placebo who took (1)  $\geq 1$  tablet from a DB rimegepant wallet, and (2) no tablets from a DB placebo wallet.
  - At least once. Defined as any of the following:
    - Randomized to rimegepant who took  $\geq 1$  tablet from a DB placebo wallet
    - Randomized to placebo who took  $\geq 1$  tablet from a DB rimegepant wallet.
- Time on DB study drug >14 weeks.

Results for all categories are displayed, even those with 0 counts.

### OL Rimegepant Treatment Compliance

The frequency table of OL rimegepant treatment compliance is provided by treatment group for the OL rimegepant safety analysis set, and displays the following categories:

- OL rimegepant tablet count compliance  $\geq 80\%$  from OL rimegepant start to later of last scheduled OLE Phase visit or OL rimegepant end. Tablet count compliance is derived as  $100 \times \text{cumulative exposure} / \text{required exposure}$ , where
  - Cumulative OL rimegepant exposure is defined in Section 6.2.6.1.
  - Required OL rimegepant exposure is derived as  $\text{integer}((n + 1)/2)$ , where  $n = \text{OL maxdate} - \text{OL rimegepant start date} + 1$ .
    - OL maxdate is defined as the latest of the (1) scheduled Week 14 and 24/EOT visit dates, and (2) OL rimegepant end date. Scheduled visits are identified from visit labels, and therefore exclude those containing “unscheduled” in the visit label.
- Average OL rimegepant exposure (tablets per month) categories:
  - >16.8 (> 20% above EOD dosing)
  - >15.4 (> 10% above EOD dosing)
  - $\geq 12.6$  to  $\leq 15.4$  ( $\pm 10\%$  of EOD dosing)
  - $\geq 11.2$  to  $\leq 16.8$  ( $\pm 20\%$  of EOD dosing)
  - $\geq 12.6$  ( $\geq 90\%$  compliant with EOD dosing)
  - $\geq 11.2$  ( $\geq 80\%$  compliant with EOD dosing)

Average OL rimegepant exposure is defined in Section 6.2.6.1.

- OL rimegepant tablets taken per month for 3 consecutive months categories:  $\geq 12$ ,  $\geq 13$ , and  $\geq 14$ 
  - Tablets per month are assessed by the number of 4-week (28-day) intervals in which a subject exceeded select OL rimegepant tablet counts from the OL rimegepant start date to the OL rimegepant end date, where the number of 4-week intervals are consecutive (see Section 6.3.1 for months).
- $>1$  OL rimegepant tablet taken on any 1 day. This is determined from the derived number of OL rimegepant tablets taken per day, which takes overlapping records into account (see Section 9.5).
- Consecutive OL rimegepant dosing days (see Section 9.5)
- Time on OL rimegepant  $>14$  weeks
- OL rimegepant start on or before DB study drug end. Defined as nonmissing OL rimegepant start date  $\leq$  DB study drug end date.
- OL rimegepant taken but DB study drug never taken. Defined as nonmissing OL rimegepant start date and missing DB study drug start date.

### **eDiary Usage Compliance During the OP and DBT Phase**

The table of eDiary usage compliance during the OP and DBT Phase is provided by treatment group for the DBT safety analysis set.

eDiary DBT usage compliance is derived as follows:

- Study drug start to later of last scheduled DBT Phase visit or DB study drug end/OL rimegepant start:  $100 \times (\text{total number of efficacy data days from the study drug start date to the DB maxdate}) / (\text{total number of days from the study drug start date to the DB maxdate})$ , where DB maxdate is defined previously.

eDiary DBT usage compliance is summarized as a continuous variable, and in the following categories:  $\geq 90\%$  compliance;  $\geq 80\%$  compliance.

In addition, the number and percentage of subjects with  $\geq 24$  days of eDiary efficacy data in the first 28 days of the OP are also displayed; see Section 7.2 for the 28-day OP analysis period and Section 9.2.2 for eDiary efficacy data days.

#### **6.2.6.3 Nonstudy Concomitant Medications**

Refer to the Core SAP for the following: definitions of select nonstudy medication types (i.e., previous, current, DBT concomitant, OL rimegepant concomitant, or follow-up); counting rules in nonstudy medication frequency tables; and nonstudy medication start and end date imputation.

The by-subject listing of nonstudy medications is provided by therapeutic class and preferred name for the enrolled analysis set. Acute migraine and prophylactic migraine medications are

identified, as well as medication type. Medications with previous inadequate response due to contraindication (see Section 9.4.2) and missing medication type are excluded.

Thes following conventions apply to nonstudy medications:

- Nonstudy medications are identified from those identified from the (1) Previous Experience With or Documented Contraindication to Prophylactic Migraine Medications CRF and (2) Concomitant Medications CRF. The Concomitant Medications CRF collects indications, and links medical history and AE terms respectively to the Medical History and AE CRFs.
- Prophylactic migraine medications are defined as nonstudy medications either (1) from the Previous Experience With or Documented Contraindication to Prophylactic Migraine Medications CRF, or (2) with an indication of “prophylactic migraine medication” from the Concomitant Medications CRF.
- Acute migraine medications are defined as nonstudy medications with either (1) an indication of “acute migraine medication” from the Concomitant Medications CRF, or (2) preferred name containing triptan, ergotamine, lasmiditan, or ubrogepant.

### **Nonstudy DBT Concomitant Medications**

Frequency tables of the following nonstudy DBT concomitant medications are provided by treatment group for the DBT safety analysis set: all; acute migraine. Medications are displayed in descending order of rimegepant frequency within therapeutic class and preferred name.

### **Nonstudy OL Rimegepant Concomitant Medications**

Frequency tables of the following nonstudy OL rimegepant concomitant medications are provided by treatment group/OL rimegepant and overall for the OL rimegepant safety analysis set: all; acute migraine. Medications are displayed in descending order of overall frequency within therapeutic class and preferred name.

## **6.3 Efficacy**

Efficacy endpoints are assessed by as-randomized treatment group.

Randomization is stratified using the RTSM system, but analyses use imputed randomization strata, which are based primarily on actual data (see Section 6.2.5.1). The rationale for using the actual data in analyses is that sites may erroneously report the wrong strata in the RTSM system. Hence, treatment group comparisons of continuous efficacy endpoints are *adjusted* by the imputed randomization strata, whereas treatment group comparisons of binary efficacy endpoints are *stratified* by the imputed randomization strata (except in subgroup analyses). If there are sparse data within a stratum, then results may be presented unstratified. Note that the phrase “randomization stratum” refers to the imputed randomization stratum throughout this section.

For binary efficacy endpoints, CIs are based on a normal approximation to the binomial distribution using asymptotic standard error (ASE). For continuous efficacy endpoints, CIs are based on the normal distribution. All CIs are 2-sided.

See Sections 7.2 and 7.3 for the definition of efficacy analysis periods and study days.

The by-subject listing of primary and key secondary efficacy endpoints is provided for the full analysis set, and includes the reason for exclusion from the migraine analysis set: randomized more than once; not treated with study drug; treated with study drug and <14 days of eDiary efficacy data in the OP; treated with study drug and <14 days of eDiary efficacy data in all 3 months of the DBT Phase. Results for continuous endpoints are based on observed data, whereas results for binary endpoints incorporate missing data imputation. Subjects with  $\geq 14$  days of eDiary efficacy data (not necessarily consecutive) in the month defining the endpoint are flagged for secondary endpoints based on a single month.

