Subjects who begin but do not complete a treatment phase (i.e., DBT or OLE Phase) must complete the corresponding End-of-Treatment (EOT) Visit (DBT EOT or OLE EOT) and the

(post-treatment) Follow-up Week 2 Visit, except in the case of withdrawal of consent, loss of a subject's ability to consent freely, death, or when a subject is lost to follow-up.

The end of the study occurs when the last study visit is completed by the last participating subject or the subject is otherwise discontinued from the study (e.g., as in the case of lost to follow-up).

Number of Subjects:

Approximately 600 subjects will be randomized in a 1:1 ratio to rimegepant or matching placebo across 2 treatment groups in the Double-blind Treatment (DBT) Phase: blinded rimegepant (75 mg ODT) (n = 300) or matching placebo (n = 300), dosed EOD. Randomization will be stratified by 1) the number of migraine days reported to have occurred during the first 28-days of the Observation Phase (4-7 or 8-14); and 2) the number of recognized, orally-administered, preventive medication categories with previous inadequate response within 10 years of the Screening Visit (due to lack of efficacy, prior intolerance, or contraindication) (2 vs. 3-4 categories).

Upon successful completion of the DBT Phase, eligible subjects will be given the opportunity to enroll into a 12-week Open-label Extension (OLE) Phase. It is estimated that approximately 480 subjects will enter the OLE Phase of the study.

Study Population:

The study will recruit subjects, ≥ 18 years of age with a minimum 1 year documented history of migraine (with or without aura), consistent with a diagnosis according to the International Classification of Headache Disorders, 3rd edition.

Per self-report, with confirmation from Investigator/supporting medical record, subjects must have:

1. Migraine attacks present for more than 1 year with the age of onset prior to 50 years of age
2. Migraine attacks, on average, lasting about 4 - 72 hours, if untreated.
3. 4 to 14 **migraine days** per month, on average, across the 3 months prior to the Screening Visit (month is defined as 28-days for the purpose of this protocol).
4. 4 to 14 migraine days during the first 28-days of the Observation Phase
5. Less than 15 **headache days** (migraine or non-migraine) per month in each of the 3-months prior to the Screening Visit and during the first 28-days of the Observation Phase.

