9.1. Sample Size

The study will randomize approximately 300 subjects per treatment group. Based on data from study BHV3000-305 and subgroup analysis from the galcanezumab Phase 3 program,^{6,9,10} we estimate that rimegepant will provide roughly a 1.0-day advantage over placebo on the primary endpoint, and assuming a common standard deviation of 3.6 days. Assuming that roughly 280 subjects per treatment group will contribute to the final migraine analysis dataset, the study will have roughly 90% power on the primary endpoint at a 2-sided alpha level of 0.05.

In study BHV3000-305, rimegepant dosed EOD provided a 1.0-day advantage over placebo dosed EOD in subjects who were not taking prophylactic migraine medication through randomization. Using the data from study BHV3000-305, the standard deviation of the primary endpoint was estimated to be roughly 3.6 days for these subjects.

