9.3.1. Efficacy Analyses

9.3.1.1. Primary Endpoint

The primary endpoint will be assessed for the DBT migraine analysis set using a linear mixed effects model with repeated measures that will include the following variables: change from the Observation Phase in the number of migraine days per month as the dependent variable; and fixed effects for treatment group, randomization stratum (i.e., 4 levels), month, and month-by-treatment group interaction. Migraine days are of any headache pain intensity. Months are defined using 4-week intervals as Month 1 (Weeks 1 to 4), Month 2 (Weeks 5 to 8), and Month 3 (Weeks 9 to 12). The number of migraine days per month is prorated to 28 days account for days with missing migraine data. The difference estimate (rimegepant – placebo), standard error (SE), p-value, and 95% confidence interval (CI) will be reported for the entire DBT Phase (Weeks 1 to 12).

The repeated measures error structure is assumed to be constant across treatment groups and will be initially specified as unstructured. If the model fails to converge or cannot be fit with an unstructured error structure, then a heterogeneous Toeplitz error structure will be attempted. If the Toeplitz fails, then an autoregressive order 1 error structure will be attempted.

The Huber-White robust “sandwich” estimator will be used for the estimation of SEs, which does not require constant response variances between treatment groups and different baseline covariate values.

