#### 6.2.5.1 *Demographics and Other Relevant Baseline Characteristics*

Refer to the Core SAP for the table of table of demographics and other relevant characteristics. Other relevant characteristics also include the following categorical variables:

- Geographic region: Australia/Europe, North America
  - North America is defined as Canada, Mexico, or United States of America.
- Previous study participation (e.g., any study, BHV3000-301, BHV3000-302, BHV3000-303, etc.)
- Randomization stratum 1 based on actual data – number of migraine days in the 28-day OP:  $<8$ ,  $\geq 8$ . These are based on absolute (not prorated) number of migraine days of total headache pain intensity during the 28-day OP analysis period (see Sections 7.2 and 9.2.5).
- **Imputed** randomization stratum 1 – number of migraine days in the 28-day OP:  $<8$ ,  $\geq 8$ .
  - If the randomization stratum 1 value based on actual data is missing, then it is imputed as follows:
    - “ $<8$ ” if the randomization stratum 1 value from the RTSM system is “4 to 7”,
    - “ $\geq 8$ ” if the randomization stratum 1 value from the RTSM system is “8 to 14”.
  - Otherwise, the imputed randomization stratum value 1 is equal to the randomization stratum 1 value based on actual data.
- Randomization stratum 2 based on actual data – number of ROM medication categories with previous inadequate response:  $<3$ ,  $\geq 3$  (see Section 9.4.2). Subcategories include 0, 1, 2, 3, 4, 3 to 4, 5, etc.
- Imputed randomization stratum 2 – number of ROM medication categories with previous inadequate response:  $<3$ ,  $\geq 3$ .
  - If the randomization stratum 2 value based on actual data is missing, then it is imputed as follows:
    - “ $<3$ ” if the randomization stratum 2 value from the RTSM system is “2”
    - “ $\geq 3$ ” if the randomization stratum 2 value from the RTSM system is “3 or 4”.
  - Otherwise, the imputed randomization stratum value 2 is equal to the randomization stratum 2 value based on actual data.
- 4-level randomization stratum based on actual data. Categories are based on randomization strata 1 and 2 based on actual data:
  - $<8$  migraine days in the 28-day OP and  $<3$  ROM medication categories with previous inadequate response

- <8 migraine days in the 28-day OP and  $\geq 3$  ROM medication categories with previous inadequate response
- $\geq 8$  migraine days in the 28-day OP and <3 ROM medication categories with previous inadequate response

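### The migraine-day model adjusts for baseline only through a stratum cut at 8 days; adding the continuous Observation Phase count would gain precision, and the stratum source should be stated alike in both documents

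*SAP*

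**What the plan says.** Protocol 9.3.1.1 models change from the OP in migraine days per month with "fixed effects for treatment group, randomization stratum (i.e., 4 levels), month, and month-by-treatment group interaction". It lists no baseline covariate and does not say whether the stratum is the value entered in the RTSM system or one derived from study data.

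SAP 6.3 settles the source: "analyses use imputed randomization strata, which are based primarily on actual data". Its reason is that sites may enter the wrong stratum in RTSM. Under SAP 6.2.5.1 the first factor is split at below 8 versus 8 or more migraine days, and "These are based on absolute (not prorated) number of migraine days of total headache pain intensity during the 28-day OP analysis period". The second factor is split at fewer than 3 versus 3 or more medication categories and comes from the prior-medication CRF (SAP 9.4.2). The RTSM value is used only if the derived value is missing.

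The example code in SAP 9.3.1 has this stratum, treatment, month and treatment-by-month on the right-hand side, and nothing else. SAP 6.5.1 and 6.5.2 add the continuous baseline score to the corresponding models for MSQ and MIBS. The same rebuilt strata serve the primary endpoint and all five key secondary endpoints. Mismatches with RTSM are cross-tabulated (SAP 6.2.5.1) and counted as protocol deviations (SAP 9.1). No efficacy analysis with the RTSM strata is planned.

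**The concern.** Two things stand out.

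First, the baseline of the primary endpoint is a count that eligibility confines to 4 to 14 days, yet the model uses only one binary cut of it. A subject with 8 OP days and one with 14 are treated as alike; subjects with 7 and 8 are not. Change is computed by subtracting the OP value, so some correlation between OP days and change is to be expected. Whatever part of it the cut does not capture stays in the residual variance. The trial's other continuous key secondary endpoints are not treated this way.

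Second, the two documents use one term for the stratum but only the SAP says what it is. Subjects are randomised in permuted blocks within RTSM strata (SAP 2.2), so a protocol reader would naturally take the term to mean those strata. With no RTSM-strata analysis planned, nobody can see whether the choice affects the result.

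At stake are some precision on the primary endpoint and on the Weeks 1 to 4 and Weeks 9 to 12 endpoints, and agreement between the documents.

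**Working it through.** **1. The plan's own figure.** Protocol 9.1 assumes "rimegepant will provide roughly a 1.0-day advantage over placebo on the primary endpoint", "assuming a common standard deviation of 3.6 days", and that "roughly 280 subjects per treatment group will contribute to the final migraine analysis dataset". SE of the difference = 3.6 × √(2/280) = 0.304. Then 1.0/0.304 = 3.287, and power = Φ(3.287 − 1.960) = 0.908. This reproduces the claim that "the study will have roughly 90% power on the primary endpoint at a 2-sided alpha level of 0.05". The calculation has no stratum term, so it does not depend on the stratum source.

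**2. Does the stratum source matter for validity?** Simulation with 560 subjects, blocks of 6 within four entered strata, total SD 3.6, and a single-outcome linear model with a 4-level stratum and sandwich SE. Assumed, because the documents give none of it: 0 to 20% entry error per factor, independent of treatment and outcome; a migraine-day stratum effect of 1.5 or 3.0 days, with 0.3 of that for the medication factor; 60% of subjects in the higher migraine-day stratum and 40% in the higher medication stratum. There were 6,000 null and 4,000 alternative replicates.

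| | RTSM strata | Rebuilt strata |
|---|---|---|
| Type I error | 0.047 to 0.055 | 0.049 to 0.057 |
| Mean estimate, true value −1.0 | about −1.0 | about −1.0 |
| Power | 0.916 to 0.956 | 0.916 to 0.961 |

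The Monte Carlo SE of the type I error is √(0.05 × 0.95/6000) = 0.003. The largest power gap is 0.9535 − 0.9315 = 0.022, in favour of the rebuilt strata, at 20% error and a 3-day effect.

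**3. What the continuous count adds.** Let r be the correlation between OP migraine days and change averaged over the DBT Phase. Let k be the share of the variance of OP days that the binary cut captures. Residual variance is proportional to 1 − kr² with the cut alone and to 1 − r² with the count added, so

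SE ratio = √[(1 − r²)/(1 − kr²)].

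For a normal variable cut at its median, k = 2/π = 0.637.

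| r (assumed) | (1 − r²)/(1 − kr²) | SE ratio | SE reduction |
|---|---|---|---|
| 0.3 | 0.910/0.943 = 0.965 | 0.983 | 1.7% |
| 0.4 | 0.840/0.898 = 0.935 | 0.967 | 3.3% |
| 0.5 | 0.750/0.841 = 0.892 | 0.944 | 5.6% |

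In sample-size terms this is 1/0.965 = 1.04 to 1/0.892 = 1.12, or about 4% to 12% more subjects.

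**4. Sensitivity to k.** Suppose OP days were spread evenly over 4 to 14. Their variance is (11² − 1)/12 = 10. The group means are 5.5 (days 4 to 7) and 11 (days 8 to 14), so the between-group variance is (4/11)(7/11)(5.5²) = 7.0 and k = 0.70. The SE reduction is then 1.5% at r = 0.3 (√(0.910/0.937) = 0.985) and 4.7% at r = 0.5 (√(0.750/0.825) = 0.953). The order of magnitude does not change.

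**5. In power terms.** If 3.6 is read as the SD after stratum adjustment (the documents do not say), power rises from 0.908 to Φ(3.287/0.983 − 1.960) = 0.917 at r = 0.3 and Φ(3.287/0.944 − 1.960) = 0.936 at r = 0.5.

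**The case against.** The best defence is that nothing here is invalid. Both stratum factors describe status before treatment: the 28-day OP window closes no later than the day before first dose in treated subjects (SAP 7.1, 7.2), and lack of efficacy or intolerance must date from before screening (SAP 9.4.2). The SAP states its choice and the reason. The protocol names no data source, the 4-level term is kept, and Protocol 9 lets the SAP adjust methods short of major changes. Correcting site errors gains a little power if anything. All of this stands.

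It also rules out some stronger readings. A reader might infer that the strata come from post-randomisation information, or that the analysis plainly departs from the protocol model. The first is wrong in substance, although CRF entries can still be corrected before lock. The second is only one reading of an unspecified term.

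A reader might also infer that the SAP's window by itself moves subjects across the 7/8 cut, because it can open the day before screening. A simulation with an assumed mean of 8.5 and SD of 2.8 days gave 3.5% to 4.9%. That figure is conditional. Headache-log entries are dated one day before the report (SAP 7.1), so a report made on the screening date falls exactly at the window start, and the shift may be zero. Nor is the unprorated count a defect: the protocol stratifies on days reported.

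The covariate proposal meets a separate objection: the protocol model does not contain it either, and r is not in the documents. Both are true. The protocol wording would therefore have to change too, and the gain must be given as a range. The covariate also does nothing for a mis-entered medication stratum, which is why the RTSM sensitivity analysis is a separate item.

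**Conclusion.** The point holds as an improvement in precision and consistency, not as a validity failure. The migraine-day model discards most of the detail in a baseline count that is already collected, while the MSQ and MIBS models keep theirs. Adding the count reduces the SE by about 1.7% to 5.6% for r between 0.3 and 0.5, whichever stratum source is used. This rests on an assumed r, on a linear relation between OP days and change, and on k of about 0.64 (a gain of 1.5% to 4.7% with k = 0.70). Below r = 0.3 the gain is negligible.

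The documents do not support the conclusion that using rebuilt strata biases the primary estimate or inflates type I error, or that RTSM strata must be primary. Over the assumed error range, type I error stays near 0.05 with either source and power differs by at most about 2 points, in favour of the SAP's choice. What remains on the strata is that the term is undefined in the protocol and that no RTSM-strata analysis is planned.

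**What to change.** Before the PCD database lock, while the study is still blinded:

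- **Covariate.** Add OP migraine days per month, the prorated value already used to compute change, as a continuous covariate beside the 4-level stratum in the model for the primary endpoint and key secondary endpoints 2 and 3. Change Protocol 9.3.1.1, SAP 6.3.1.3 and the SAP 9.3.1 code together. Every subject in the migraine analysis set has at least 14 OP diary days, so the main analysis loses nobody.
- **Imputation models.** The jump-to-reference and tipping-point analyses reuse the main model, so add the same covariate to their imputation models. They run on the wider DBT efficacy set, so also state how a subject without an evaluable OP value is handled.
- **Definition.** Define randomization stratum in the same words in both documents, including the fallback to RTSM values.
- **Sensitivity analysis.** Prespecify a repeat of the primary and all five key secondary analyses with the RTSM strata.

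The cost is one model term, a matching protocol wording change and one extra model run per endpoint. The RTSM strata and OP counts are already held.
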